#### **3.6.3. Definition of Study Day**

The first dose date of VBR when administered in combination with ETV with or without Peg-IFN $\alpha$  will be calculated where applicable. Study Day 1 is defined as the first dose date of study drug, which is the earliest/minimum of the first dose dates of VBR, ETV, and Peg-IFN $\alpha$  in a treatment group. If the first dose date is missing, the date of randomization will be used.

The last dose date of VBR, ETV, and of Peg-IFN $\alpha$  will be calculated where applicable. For the Randomized Treatment Phase, the last dose date of study drug VBR will be the Week 24 visit date or the end date on study drug administration CRF if a subject discontinued study drug prior to Week 24 visit. For study drug ETV, the last dose date will be obtained from End of Treatment-ETV eCRF. For study drug Peg-IFN $\alpha$ , the last dose date will be obtained from End of Treatment-Peg-IFN $\alpha$  eCRF. For the Overall Treatment Phase, the last dose date for each drug will be the end date on the respective End of Treatment eCRF pages. The last dose date of study drug will be defined as the latest/maximum of the last dose dates of VBR, ETV, and Peg-IFN $\alpha$  in a treatment group.

For the on-treatment phases, Study Day will be calculated from Study Day 1 and derived as follows:

- For days prior to the first dose: Assessment Date – Study Day 1
- For postdose study days: Assessment Date – Study Day 1 + 1

For the Follow-up Phase, the follow-up Study Day 1 is defined as the day after Week 48 visit or Premature Termination visit. The follow-up study day will be derived as Assessment Date – follow-up Study Day 1 +1.

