### 3.6.4. Analysis Visit Windows

Subject visits might not occur on protocol-specified days. Therefore, for the purpose of analysis, observations will be assigned to analysis windows. In general, the baseline value will be the last nonmissing value on or prior to the first dose date of study drug. The on-treatment phases include Randomized Treatment Phase and Overall Treatment Phase. For the Randomized Treatment Phase, the data will be summarized up to the Week 24 visit or premature termination visit. For the Overall Treatment Phase, the data will be summarized up to the Week 48 visit or premature termination visit. For the Follow-up Phase, the data will be summarized from follow-up Study Day 1 through the end of study, where Follow-Up Baseline data is from Week 48 visit or premature termination visit.

The analysis windows for the on-treatment HBV DNA and HBV pgRNA assessments are provided in Table 3-1.

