**Table 3-4** **On-Treatment Analysis Visit Windows for Urinalysis**

Nominal Visit	On-Treatment Nominal Study Day	Visit Window Study Day	
		Lower Limit	Upper Limit
Day 1	1	(none)	1
Week 4	28	2	42
Week 8	56	43	70

Nominal Visit	On-Treatment Nominal Study Day	Visit Window Study Day	
		Lower Limit	Upper Limit
Week 12	84	71	98
Week 16	112	99	126
Week 20	140	127	154
Week 24	168	155	252
Week 48	336	253	≥336

The analysis windows for on-treatment electrocardiograms (ECG) measurements are provided in Table 3-5.

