**Table 3-5 On-Treatment Analysis Visit Windows for ECG**

Nominal Visit	On-Treatment Nominal Study Day	Visit Window Study Day	
		Lower Limit	Upper Limit
Day 1	1	(none)	1
Week 12	84	2	126
Week 24	168	127	252
Week 48	336	253	≥336

The analysis windows for Follow-up Phase study assessments of efficacy (except HBsAb and HBeAb), vital signs, and laboratory assessments (chemistry, hematology, coagulation and urinalysis) are provided in Table 3-6.

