### 3.6.5. Selection of Data in the Event of Multiple Records in an Analysis Visit Window

Depending on the statistical analysis method, single values may be required for each analysis window. If a single value is needed, but multiple valid, nonmissing measurements exist in an analysis window, records will be chosen based on the following rules:

- For Baseline, the last nonmissing value on or prior to the first dose date of study drug will be selected, unless specified differently. If there are multiple records with the same time or no time recorded on the same day, the record with the lowest accession number will be selected as the baseline value.
- For postbaseline values:
  - The record closest to the nominal day for that visit will be selected with the exception of virology parameters in which the latest record will be selected.
  - If there are 2 records that are equidistant from the nominal day, the later record will be selected.
  - If there is more than 1 record on the selected day with the same time, the retest record will be selected. If there is no clear indication for which record is the retest record, then the record with the lowest accession number will be selected.

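### The SAP's follow-up day formula puts the Follow-Up Baseline visit on Day 0, which no window in Table 3-6 or 3-7 contains

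*Combined protocol and SAP*

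**What the plan says.** SAP 3.6.3 fixes the anchor: "the follow-up Study Day 1 is defined as the day after Week 48 visit or Premature Termination visit". It then gives one formula for the follow-up phase: "The follow-up study day will be derived as Assessment Date – follow-up Study Day 1 +1". A separate rule for earlier dates, "For days prior to the first dose: Assessment Date – Study Day 1", appears in the same section but is introduced for the on-treatment phases only.

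SAP 3.6.4 identifies the record meant to serve as the follow-up reference: "where Follow-Up Baseline data is from Week 48 visit or premature termination visit".

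Table 3-6 (efficacy other than HBsAb and HBeAb, vital signs, laboratory) and Table 3-7 (ECG) both give FU-Baseline a nominal day of -1, no lower limit and an upper limit of -1. The next window starts at Day 1: FU-Week 4 in Table 3-6 and FU-Week 12 in Table 3-7.

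SAP 3.6.5 governs multiple post-baseline records in one window: "The record closest to the nominal day for that visit will be selected with the exception of virology parameters", for which the latest record is used. Ties are settled by "If there are 2 records that are equidistant from the nominal day, the later record will be selected".

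**The concern.** The formula and the tables appear to number the same visit differently, by one day. If so, the record that defines FU-Baseline is excluded from FU-Baseline for every subject and every parameter in the two tables.

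Because that window has no lower limit, a literal program need not leave the row blank. It could pick up an older on-treatment record and label it as the follow-up reference. Either outcome contradicts SAP 3.6.4.

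A second effect concerns subjects who stop early. Protocol 7.9 requires an ECG and urinalysis at the PT visit. The on-treatment windows for these two are wide, and a PT record can lose its slot there to a scheduled record. FU-Baseline is then its only other by-visit position. SAP Section 1 says the study was terminated and participants went from treatment into follow-up, so PT visits are plausible, although their number is not given.

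**Working it through.** **Inputs**
- Nominal study days (SAP Tables 3-1 to 3-5): Week 12 = 84, Week 24 = 168, Week 28 = 196, Week 44 = 308, Week 48 = 336.
- Visit windows (Protocol 7.5 and 7.6): ±3 days, except -3 days only at Weeks 24 and 48.
- Urinalysis, Week 24 window (Table 3-4): Days 155–252; Week 48 from Day 253.
- ECG windows (Table 3-5): Week 12, Days 2–126; Week 24, Days 127–252; Week 48 from Day 253.

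**1. Follow-up day of the anchor visit.** Let V be the date of the Week 48 or PT visit. Follow-up Day 1 is V + 1.
- Stated formula: V - (V + 1) + 1 = 0. The tabulated value is -1, so it is not reproduced.
- Branch without the +1: V - (V + 1) = -1. This matches the tables, but SAP 3.6.3 does not state it for follow-up.

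With Week 48 on Day 336, follow-up Day 1 is Study Day 337:

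| Visit | Study day | Stated formula | Window in Table 3-6 |
|---|---|---|---|
| Week 44 | 308 | 308 - 337 + 1 = -28 | FU-Baseline |
| Week 48 | 336 | 336 - 337 + 1 = 0 | none |
| Week 52 | 364 | 364 - 337 + 1 = 28 | FU-Week 4 |
| Week 56 | 392 | 392 - 337 + 1 = 56 | FU-Week 8 |
| Week 60 | 420 | 420 - 337 + 1 = 84 | FU-Week 12 |

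Repeating this with Week 48 on Day 333 and with a PT visit on Day 200 also gives Day 0. The later follow-up days agree with the tables, so the fault is confined to FU-Baseline. The on-treatment windows in Tables 3-1 to 3-5 have no gaps, so the visit always has an on-treatment window.

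**2. PT records left with no by-visit slot.** A PT record displaces the scheduled one only if it is at least as close to the nominal day.
- ECG and urinalysis against Week 24: the scheduled record is on Days 165–168, a distance of 0 to 3. From Day 172 (distance 4) to Day 252 the PT record is never selected: 252 - 172 + 1 = 81 days.
- ECG against Week 12: the scheduled record is on Days 81–87, a distance of at most 3. From Day 88 to Day 126 the PT record is never selected: 126 - 88 + 1 = 39 days.
- Vital signs, chemistry, hematology and coagulation: shorter intervals. Against Week 28 (window 183–210, visit on Days 193–199), the interval is Days 200–210.
- A PT ECG or urinalysis from Day 253 falls in the Week 48 window and keeps a slot.
- Virology takes the latest record, so it is not exposed.

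**3. Age of the record if the open FU-Baseline window is filled literally** (nearest earlier scheduled record)
- Four-weekly parameters, Week 44 (Days 305–311) before Week 48 (Days 333–336): 333 - 311 = 22 to 336 - 305 = 31 days.
- ECG and urinalysis, Week 24 before Week 48: 333 - 168 = 165 to 336 - 165 = 171 days.
- ECG and urinalysis, Week 24 before a PT visit on Days 172–252: 172 - 168 = 4 to 252 - 165 = 87 days.

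Unscheduled records could be closer.

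**The case against.** The strongest reply is that SAP 3.6.4 assigns Follow-Up Baseline by named visit, so no day calculation is needed. Also, SAP 3.6.2 starts the Follow-up Phase after the Week 48 or PT visit, so Day 0 comes from applying the formula outside its phase. On that reading the tabulated -1 simply carries over the on-treatment convention of having no Day 0. The intent is indeed recoverable, and a careful programmer would probably reach it. But SAP 3.6.4 also says that observations are assigned to analysis windows, and the windows contradict its own sentence. If the formula does not cover this visit, no stated rule produces -1. The text needs repair either way. The record ages in step 3 arise only if the named-visit sentence is ignored.

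A second reply is that the ECG and urinalysis loss comes from wide on-treatment windows and the closest-record rule, not from the day label. That is half right. Those rules remove the on-treatment slot, and the numbering removes the remaining one. Correcting the numbering restores a by-visit place only if an FU-Baseline row is displayed. Table 3-7 lists FU-Baseline as a visit, and SAP 7.5 plans an ECG shift table by visit, but no text says explicitly that the row will appear. For urinalysis the by-visit summary is a protocol display (Protocol 10.3.6.2). The SAP specifies no such table, and the reduced synoptic report may omit it.

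The safeguards also stand. Clinically significant ECG findings (once confirmed) and laboratory findings are to be recorded as adverse events (Protocol Appendix 1 and Section 8.5), by-subject listings are planned, and graded laboratory summaries use the worst post-baseline value (SAP 7.2.1.2).

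**Conclusion.** The concern holds. Under the stated formula the Week 48 or PT visit is follow-up Day 0, one day outside the FU-Baseline window, for every parameter in Tables 3-6 and 3-7. It is a minor correction, but it should be made.

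The consequence is a blank or wrongly filled FU-Baseline row. For PT visits in the intervals above (81 days for ECG and urinalysis, a further 39 days for ECG), a safety record can also be missing from by-visit displays. Those intervals assume that the scheduled record was taken inside its protocol visit window. How many subjects are affected cannot be computed, because the documents do not give the number or timing of PT visits.

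No analysis of change from FU-Baseline is specified. Changes from pre-dose Baseline, the later follow-up windows and the treatment comparisons do not depend on this numbering.

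**What to change.** Either of two edits closes the gap:

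1. In SAP 3.6.3, add that for dates before follow-up Study Day 1 the follow-up day is the assessment date minus follow-up Study Day 1, with no 1 added. The Week 48 or PT visit becomes Day -1, as tabulated.
2. Keep the formula and change the FU-Baseline nominal day and upper limit from -1 to 0 in Tables 3-6 and 3-7.

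With either edit, restrict FU-Baseline to the Week 48 or PT visit record, in line with SAP 3.6.4, instead of leaving the lower limit open. State also whether FU-Baseline appears as a row in the by-visit ECG and laboratory displays.

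Follow-up Days 28, 56 and 84 do not change under either edit. The numbering edit costs one line of text, or two cells in each of two tables. The restriction and the display statement need a short clarification, and there is one programming check. No new data or analyses are needed.

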### 3.6.4. Analysis Visit Windows

Subject visits might not occur on protocol-specified days. Therefore, for the purpose of analysis, observations will be assigned to analysis windows. In general, the baseline value will be the last nonmissing value on or prior to the first dose date of study drug. The on-treatment phases include Randomized Treatment Phase and Overall Treatment Phase. For the Randomized Treatment Phase, the data will be summarized up to the Week 24 visit or premature termination visit. For the Overall Treatment Phase, the data will be summarized up to the Week 48 visit or premature termination visit. For the Follow-up Phase, the data will be summarized from follow-up Study Day 1 through the end of study, where Follow-Up Baseline data is from Week 48 visit or premature termination visit.

The analysis windows for the on-treatment HBV DNA and HBV pgRNA assessments are provided in Table 3-1.

**Table 3-1 On-Treatment Analysis Visit Windows for HBV DNA and pgRNA**

Nominal Visit	On-Treatment Nominal Study Day	Visit Window Study Day	
		Lower Limit	Upper Limit
Day 1	1	(none)	1
Week 1	7	2	10
Week 2	14	11	21
Week 4	28	22	35

Nominal Visit	On-Treatment Nominal Study Day	Visit Window Study Day	
		Lower Limit	Upper Limit
Week 6	42	36	49
Week 8	56	50	70
Week 12	84	71	98
Week 16	112	99	126
Week 20	140	127	154
Week 24	168	155	182
Week 28	196	183	210
Week 32	224	211	238
Week 36	252	239	266
Week 40	280	267	294
Week 44	308	295	322
Week 48	336	323	≥336

The analysis windows for the on-treatment assessments of vital signs, chemistry, and hematology are provided in Table 3-2.

**Table 3-2** On-Treatment Analysis Visit Windows for Vital Signs, Chemistry, and Hematology

Nominal Visit	On-Treatment Nominal Study Day	Visit Window Study Day	
		Lower Limit	Upper Limit
Day 1	1	(none)	1
Week 2	14	2	21
Week 4	28	22	42
Week 8	56	43	70
Week 12	84	71	98
Week 16	112	99	126
Week 20	140	127	154
Week 24	168	155	182
Week 28	196	183	210
Week 32	224	211	238
Week 36	252	239	266
Week 40	280	267	294

Nominal Visit	On-Treatment Nominal Study Day	Visit Window Study Day	
		Lower Limit	Upper Limit
Week 44	308	295	322
Week 48	336	323	$\geq 336$

The analysis windows for the on-treatment HBsAg, HBeAg, HBcrAg, and coagulation assessments are provided in Table 3-3.

**Table 3-3** **On-Treatment Analysis Visit Windows for HBsAg, HBeAg, HBcrAg, and Coagulation**

Nominal Visit	On-Treatment Nominal Study Day	Visit Window Study Day	
		Lower Limit	Upper Limit
Day 1	1	(none)	1
Week 4	28	2	42
Week 8	56	43	70
Week 12	84	71	98
Week 16	112	99	126
Week 20	140	127	154
Week 24	168	155	182
Week 28	196	183	210
Week 32	224	211	238
Week 36	252	239	266
Week 40	280	267	294
Week 44	308	295	322
Week 48	336	323	$\geq 336$

The analysis windows for the on-treatment urinalysis assessments are provided in Table 3-4.

**Table 3-4** **On-Treatment Analysis Visit Windows for Urinalysis**

Nominal Visit	On-Treatment Nominal Study Day	Visit Window Study Day	
		Lower Limit	Upper Limit
Day 1	1	(none)	1
Week 4	28	2	42
Week 8	56	43	70

Nominal Visit	On-Treatment Nominal Study Day	Visit Window Study Day	
		Lower Limit	Upper Limit
Week 12	84	71	98
Week 16	112	99	126
Week 20	140	127	154
Week 24	168	155	252
Week 48	336	253	≥336

The analysis windows for on-treatment electrocardiograms (ECG) measurements are provided in Table 3-5.

**Table 3-5 On-Treatment Analysis Visit Windows for ECG**

Nominal Visit	On-Treatment Nominal Study Day	Visit Window Study Day	
		Lower Limit	Upper Limit
Day 1	1	(none)	1
Week 12	84	2	126
Week 24	168	127	252
Week 48	336	253	≥336

The analysis windows for Follow-up Phase study assessments of efficacy (except HBsAb and HBeAb), vital signs, and laboratory assessments (chemistry, hematology, coagulation and urinalysis) are provided in Table 3-6.

**Table 3-6 Follow-Up Analysis Visit Windows for Efficacy, Vital Signs, and Laboratory Assessments**

Nominal Visit	Off-Treatment Nominal Study Day	Visit Window Study Day	
		Lower Limit	Upper Limit
FU-Baseline	-1	(none)	-1
FU-Week 4	28	1	42
FU-Week 8	56	43	70
FU-Week 12	84	71	≥126

The analysis windows for Follow-Up Phase ECG is provided in.

**Table 3-7** Follow-Up Analysis Visit Windows for ECG

Nominal Visit	Off-Treatment Nominal Study Day	Visit Window Study Day	
		Lower Limit	Upper Limit
FU-Baseline	-1	(none)	-1
FU-Week 12	84	1	$\geq 126$

### 3.6.5. Selection of Data in the Event of Multiple Records in an Analysis Visit Window

Depending on the statistical analysis method, single values may be required for each analysis window. If a single value is needed, but multiple valid, nonmissing measurements exist in an analysis window, records will be chosen based on the following rules:

- For Baseline, the last nonmissing value on or prior to the first dose date of study drug will be selected, unless specified differently. If there are multiple records with the same time or no time recorded on the same day, the record with the lowest accession number will be selected as the baseline value.
- For postbaseline values:
  - The record closest to the nominal day for that visit will be selected with the exception of virology parameters in which the latest record will be selected.
  - If there are 2 records that are equidistant from the nominal day, the later record will be selected.
  - If there is more than 1 record on the selected day with the same time, the retest record will be selected. If there is no clear indication for which record is the retest record, then the record with the lowest accession number will be selected.

## 4. SUBJECT DISPOSITION

### 4.1. Subject Enrollment and Disposition

A summary of subject enrollment will be provided by treatment group for each country, investigator within a country, and overall. The summary will present the number and percentage of subjects enrolled. For each column, the denominator for the percentage calculation will be the total number of subjects analyzed for that column.

A similar enrollment table will be provided by randomization stratum. The denominator for the percentage of subjects in the stratum will be the total number of randomized subjects. If there are discrepancies in the value used for stratification assignment between the IRT and the clinical database, the value collected in the clinical database will be used for the summary. A listing of subjects with discrepancies in the value used for stratification assignment between the IRT and the clinical database at the time of data finalization will be provided. The randomization schedule used for the study will be provided as an appendix to the CSR.

A summary of subject disposition will be provided by treatment group. This summary will present the number of subjects in each of the categories listed below:

- All Randomized Analysis Set
- Full Analysis Set
- Safety Analysis Set

The number and percentage of the subjects in the following categories will be summarized using the Safety Analysis Set:

- Continuing study drug VBR
- Completed study drug VBR
- Did not complete study drug VBR and reasons for study drug discontinuation
- Continuing study drug ETV
- Completed study drug ETV
- Did not complete study drug ETV and reasons for study drug discontinuation
- Continuing study drug Peg-IFN $\alpha$
- Completed study drug Peg-IFN $\alpha$
- Did not complete study drug Peg-IFN $\alpha$  and reasons for study drug discontinuation

- Continuing study
- Completed study
- Did not complete the study and reasons for study discontinuation

For the status of study drug and study completion and reasons for discontinuation, the number and percentage of subjects in each category will be provided. The denominator for the percentage calculation will be the total number of subjects in the Safety Analysis Set corresponding to that column.

The following by-subject listings will be provided by subject number in ascending order:

- Reasons for premature study drug or study discontinuation
- Dispensed bottle number and lot number for VBR, lot number for Peg-IFN $\alpha$  and ETV

## **4.2. Extent of Study Drug Exposure and Compliance**

Extent of exposure to study drug will be examined by assessing the total duration of exposure to study drug and the level of compliance relative to the study drug regimen specified in the protocol.

### **4.2.1. Duration of Exposure to Study Drug**

Total duration of exposure to each study drug through Week 24 will be defined as the last dose date at Week 24 minus the first dose date plus 1 for VBR and for ETV, plus 7 for Peg-IFN $\alpha$ , regardless of any temporary interruptions in study drug administration, and will be expressed in weeks using up to 1 decimal place (eg, 4.5 weeks). Duration (weeks) = Duration (days) / 7. Total duration of exposure to VBR through Week 48 will also be summarized and defined as the last dose date of VBR minus the first dose date plus 1 for VBR, similar calculation will be performed for total duration of ETV exposure. The last dose date of individual study drug is defined in [Section 3.6.3](#). If the last study drug dose date is missing, the latest date among the study drug end date, clinical visit date, laboratory sample collection date, and vital signs assessment date that occurred during the on-treatment period will be used for subjects included in the final analyses or the last available date in the database snapshot for subjects who were still on treatment at the time of an interim analysis.

The total duration of exposure to study drug will be summarized using descriptive statistics. Summaries will be provided by treatment group in each on-treatment phase for the Safety Analysis Set. For the Randomized Treatment Phase, the expected total duration of Randomized Treatment Phase for all subjects is 24 weeks. The distribution of subjects by the total number of weeks on therapy (ie,  $\leq$ 4 weeks, >4-8 weeks, >8-12 weeks, >12-16 weeks, >16-20 weeks, >20-24 weeks, and  $\geq$ 24 weeks) will be presented. After completion of the randomized treatment, all subjects will receive VBR+ETV for an additional 24 weeks. For the Overall Treatment Phase, the duration of exposure to VBR and ETV will be summarized. The expected total duration of

Overall Treatment Phase for all subjects is 48 weeks. The distribution of subjects by the total number of weeks on therapy (ie,  $\leq 12$  weeks,  $> 12-24$  weeks,  $> 24 - < 48$  weeks, and  $\geq 48$  weeks) will be presented.

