- Study drug administration (731, ETV and Peg-IFN $\alpha$  [as applicable])

The following assessments must be completed postdose on Day 1:

- Provide dosing diary to subjects
- Study drug dispensation (731, ETV, and Peg-IFN $\alpha$  [as applicable])
- PK samples: postdose samples for 731, Peg-IFN $\alpha$ , and ETV between 2 and 4 hours following study drug administration ([Section 7.11](#))

#### 7.4. Study Week 1

The following assessments are performed at Study Week 1:

- Symptom-directed physical examination
- Review concomitant medications
- Review AEs
- Laboratory analyses (additional details are provided in the Laboratory Manual):
  - Virology: HBV DNA, HBV pgRNA, sample for HBV sequencing and HBV nucleic acids ([Appendix 2](#))
- Review dosing diary and assess drug accountability

#### 7.5. Study Weeks 2 Through 24

The following assessments are performed at Study Weeks 2, 4, 6, 8, 12, 16, 20, and 24 (inclusive) unless otherwise indicated. Subjects who discontinue treatment before Week 24 should immediately undergo the assessments listed for the Premature Termination Visit and then continue the scheduled follow-up assessments. A visit window of  $\pm 3$  days is applied to each visit through Week 20. A visit window of -3 days is applied to Week 24 ([Appendix 1](#)).

- Liver staging (Week 24 only)
- Measure body weight (Week 24 only)
- Vital signs (temperature, heart rate, respiration rate, and blood pressure; not at Week 6)
- Complete physical examination (excluding breast and genitalia, unless indicated; Week 24 only)
- Symptom-directed physical examination (not at Week 24)
- 12-lead ECG (Weeks 12 and 24 only)
- Review concomitant medications
- Review AEs
- Laboratory analyses (additional details are provided in the Laboratory Manual):
  - Safety labs: chemistry (not at Week 6), hematology (not at Week 6), coagulation (not at Week 2 or 6), TSH (only at Weeks 12 and 24), urinalysis (not at Week 2 or 6), urine pregnancy test (not at Week 6) ([Appendix 2](#))
  - Virology: HBV DNA, HBV pgRNA, HBsAg (not at Week 2 or 6), HBeAg (not at Week 2 or 6), HBcAg (not at Week 2 or 6), HBsAb and HBeAb (Weeks 12 and 24 only), sample for HBV sequencing and HBV nucleic acids ([Appendix 2](#))

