- PK samples: samples for 731, Peg-IFN $\alpha$ , and ETV between 30 min and 2 hours postdose at Weeks 2, 8, 12, and 24, and between 4 and 6 hours postdose at Weeks 16 and 20. Predose samples for 731, Peg-IFN $\alpha$ , and ETV will be collected at Week 4 and Week 24 only ([Section 7.11](#))
- Review dosing diary and assess drug accountability
- Study drug dispensation (not at Weeks 2 and 6; Peg-IFN $\alpha$  will not be dispensed at Week 24)
- Study drug administration (731 and ETV in-clinic [except at Weeks 2 and 6]; Peg-IFN $\alpha$  may be administered at home)

## 7.6. Study Weeks 28 Through 48

The following assessments are performed at Study Weeks 28, 32, 36, 40, 44, and 48 (inclusive) unless otherwise indicated. Subjects who discontinue treatment before Week 48 should immediately undergo the assessments listed for the Premature Termination Visit and then continue the scheduled follow-up assessment. A visit window of  $\pm 3$  days is applied to each visit through Week 44. A visit window of -3 days is applied to Week 48 ([Appendix 1](#)).

- Liver staging (Week 48 only)
- Measure body weight (Week 48 only)
- Vital signs (temperature, heart rate, respiration rate, and blood pressure)
- Complete physical examination (excluding breast and genitalia, unless indicated; Week 48 only)
- Symptom-directed physical examination (not at Week 48)
- 12-lead ECG (Week 48 only)
- Review concomitant medications
- Review AEs
- Laboratory analyses (additional details are provided in the Laboratory Manual):
  - Safety labs: chemistry, hematology, coagulation, urinalysis (Week 48 only), urine pregnancy test ([Appendix 2](#))
  - Virology: HBV DNA, HBV pgRNA, HBsAg, HBeAg, HBcAg, HBsAb and HBeAb (Week 48 only), sample for HBV sequencing and HBV nucleic acids ([Appendix 2](#))
- PK samples: samples for ETV may be collected predose at Week 44 ([Section 7.11](#))
- Study drug administration (731 and ETV)
- Review dosing diary and assess drug accountability
- Study drug dispensation (only ETV will be dispensed at Week 48, not 731)

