##### 4.2.2.1. On-Treatment Compliance

The level of on-treatment compliance to the study drug will be determined by the total amount of study drug administered relative to the total amount of study drug expected to be administered during a subject's actual on-treatment period.

The level of on-treatment compliance for each study drug will be expressed as a percentage using the following formula:

$$\text{On-Treatment Compliance (\%)} = \left( \frac{\text{Total Amount of Study Drug Administered}}{\text{Total Amount of Study Drug Expected to be Administered On Treatment}} \right) \times 100$$

Per protocol, each subject completing treatment and receiving VBR is expected to take three 100 mg tablets of VBR daily during the Randomized Treatment Phase (ie, a total of 504 tablets is expected in a 24-week period) and during the Overall Treatment Phase (ie, a total of 1008 tablets are expected in a 48-week period). Each subject completing treatment and receiving ETV is expected to take a single oral 0.5 mg tablet once daily during the Randomized Treatment Phase (ie, a total of 168 tablets is expected in a 24-week period), during the Overall Treatment Phase

(ie, a total of 336 tablets are expected in a 48-week period). Each subject completing treatment and receiving Peg-IFN $\alpha$  is expected to have a total of 24 syringes of Peg-IFN $\alpha$  administered.

For subjects who prematurely discontinue, the denominator will be the total amount of study drug expected to be administered by the date of premature discontinuation.

Descriptive statistics for the level of on-treatment compliance with the number and percentage of subjects belonging to compliance categories (eg, <=80%, > 80-90%, and  $\geq$  90%) will be provided by treatment group for the Safety Analysis Set.

A by-subject listing of study drug administration and drug accountability will be provided separately by subject ID number in ascending order and visit in chronological order.

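### The Randomized Treatment Phase exposure bands in SAP 4.2.1 overlap at exactly 24.0 weeks, the planned duration, so a subject exactly on schedule is counted twice

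*Combined protocol and SAP*

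**What the plan says.** SAP 4.2.1 lists seven bands for weeks on therapy in the Randomized Treatment Phase. They start at 4 weeks or less and finish ">8-12 weeks, >12-16 weeks, >16-20 weeks, >20-24 weeks, and" 24 weeks or more. The list is introduced by 'ie', so it is a definition and not an example. The same section gives 24 weeks as the expected length of this phase.

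Duration is the "last dose date at Week 24 minus the first dose date plus 1 for VBR and for ETV, plus 7 for Peg-IFN"α, and it "will be expressed in weeks using up to 1 decimal place". For VBR in this phase, SAP 3.6.3 sets the end point: "the last dose date of study drug VBR will be the Week 24 visit date", or the recorded end date if the subject stopped earlier. Protocol 7.5 lets that visit be early but not late: "A visit window of -3 days is applied to Week 24". Protocol 7.6 does the same at the end of treatment: "A visit window of -3 days is applied to Week 48".

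For the longer phase, SAP 4.2.1 states that the expected total duration of the "Overall Treatment Phase for all subjects is 48 weeks". Its bands are 12 or less, `>12-24`, `>24-<48` and 48 or more. These do not overlap.

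SAP 4.2.2.1 will also report "the number and percentage of subjects belonging to compliance categories". Here the bands are introduced by 'eg': 80% or less, `>80-90%`, and 90% or more.

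**The concern.** A banded table should place each subject in one row. Here the upper edge of one band and the lower edge of the next are both inclusive at 24 weeks. The shared value is the one that the dosing schedule is built to produce, so it is likely to occur in practice.

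A programmer who follows the text counts such subjects in two rows. One who notices the overlap must choose a row without a rule. In a study that was stopped early, this distribution is one of the places where a reader looks to see how many subjects received the full randomized course, so the top two rows should be unambiguous.

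**Working it through.** **Inputs.** Peg-IFN once weekly (protocol 6.2.3), with 24 syringes expected (SAP 4.2.2.1). Duration formula and bands (SAP 4.2.1). VBR end point (SAP 3.6.3). Week 24 and Week 48 as nominal Days 168 and 336 (SAP Table 3-1). Visit windows of -3 days (protocol 7.5 and 7.6).

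**1. The plan's own expected amounts.** VBR: 3 × 168 = 504 and 3 × 336 = 1008 tablets. ETV: 168 and 336 tablets. Peg-IFN: 24 syringes. All agree with SAP 4.2.2.1.

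**2. Peg-IFN, 24 weekly doses from Day 1.** Dose 24 falls on Day 1 + 23 × 7 = 162. Duration = 162 − 1 + 7 = 168 days, and 168/7 = 24.0 weeks.

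| Last dose | Days | Weeks | Band(s) |
|---|---|---|---|
| 1 day early | 167 | 23.9 | `>20-24` |
| On schedule | 168 | 24.0 | `>20-24` and `≥24` |
| 1 day late | 169 | 24.1 | `≥24` |

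**3. VBR, first dose on Day 1, last dose date = Week 24 visit.** Duration in days equals the study day of the visit.

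| Visit day | Weeks | Band(s) |
|---|---|---|
| 165 | 165/7 = 23.6 | `>20-24` |
| 166 | 166/7 = 23.7 | `>20-24` |
| 167 | 167/7 = 23.9 | `>20-24` |
| 168 | 168/7 = 24.0 | `>20-24` and `≥24` |

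If sites take the target as Day 169 instead, the permitted days are 166 to 169 and Day 169 gives 24.1 weeks, in the top band only. Under either convention, one of the four permitted days is counted twice.

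**4. Rounding.** Days 167 and 169 round to 23.9 and 24.1. One-decimal rounding therefore neither widens nor removes the overlap, which sits at 168 days alone.

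**5. Effect on the table.** If k of n subjects in a group have exactly 168 days, the rows sum to (n + k)/n. About 60 subjects randomized 1:1:1 gives n of about 20, so each double count adds 1/20 = 5 percentage points.

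**6. Overall Treatment Phase.** If the last VBR dose is at a Week 48 visit on Day 333, 334, 335 or 336, exposure is 47.6, 47.7, 47.9 or 48.0 weeks. The first three fall in `>24-<48` only and the last in `≥48` only. There is no double count.

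**7. Compliance at exactly 90%.** On the full totals, 90% would need 453.6 of 504, 907.2 of 1008, 151.2 of 168, 302.4 of 336, or 21.6 of 24. None is a whole number, so the tie cannot occur unrounded on those totals. It can occur for an early discontinuer (9 of 10 syringes, for example) or after rounding. A VBR subject who takes every dose to a Day 165 visit has 495/504 = 98.2% even against the fixed 24-week total, so stays in the top band.

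**The case against.** The strongest reply is that this is a one-character slip that any programmer would settle, in a descriptive table, in a study with no formal inference. On the size of the problem that is right. It is also fair that the Peg-IFN double count needs exactly 168 days. Injections after the first are given at home, and a last dose one day early or late removes it. The documents do not say how many subjects will land on that day. None of this makes the two bands exclusive.

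Three stronger readings are tempting, and the documents do not support them.

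- **That most VBR completers would appear as incomplete.** No exposure band is labelled as completion. SAP 4.1 tabulates completion and non-completion of VBR separately. A last dose on Days 165 to 167 really is 23.6 to 23.9 weeks of exposure, and the band reports it correctly. A count of permitted visit days is not a proportion of patients: visit timing is not given, and SAP 3.6.4 expects some visits off schedule (Table 3-1 accepts Week 24 up to Day 182). At Week 48, SAP 3.6.3 takes the last dose date from the End of Treatment eCRF and not from the visit date.
- **That the top compliance band misses completers.** It does not, as step 7 shows, and those bands are only examples.
- **That the primary safety results are affected.** SAP 7.1.6 bases adverse event summaries on the Safety Analysis Set. SAP 7.2.1.2 bases laboratory percentages on subjects with postbaseline values. Neither uses an exposure band.

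**Conclusion.** Wrong as written, and minor. The overlap at 24.0 weeks follows from the text alone. It falls on the planned duration for an exactly on-schedule Peg-IFN subject and for a VBR subject seen on Day 168. The number of subjects affected cannot be known from the documents; it is the number with a duration of exactly 168 days. The 5-point figure per subject assumes the planned group size of about 20.

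The overlap at 90% compliance is real but smaller, because its bands are illustrative and it does not touch full-dose completers. The consequence is confined to the row counts and percentages of descriptive exposure and compliance tables. Summary statistics of duration, safety denominators and the treatment comparisons are unchanged.

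**What to change.** In SAP 4.2.1, write the last two Randomized Treatment Phase bands as `>20-<24 weeks` and `≥24 weeks`. In SAP 4.2.2.1, write `>80-<90%` and `≥90%`. Both then match the style already used for the Overall Treatment Phase.

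Optionally, add a footnote to the exposure table. It would say that the -3 day visit window allows a subject who completed VBR per protocol to show 23.6 to 23.9 weeks (or 47.6 to 47.9 weeks if the last dose is at an early Week 48 visit), and that completion is reported in the disposition table.

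Do not move the band edges to allow for the window. Starting the top bands at 165 and 333 days while the bands below still run to 24 and 48 weeks would put Days 165 to 167 and 333 to 335 in two rows, which is a wider overlap than the present one.

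The cost is SAP wording and table shells. No data collection or analysis method changes. If the SAP is already final, SAP 1 provides the route: record the change in the Synoptic CSR.
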